8.3.2. Post-Study adverse events and serious adverse events

A post-study AE/SAE is defined as any event that occurs outside of the AE/SAE reporting period defined in [Table 11](#). Investigators are not obligated to actively seek AEs or SAEs in former study participants. However, if the investigator learns of any SAE at any time after a subject has been discharged from the study, and he/she considers the event reasonably related to the study vaccines, the investigator will promptly notify the Study Contact for Reporting SAEs.

8.3.3. Evaluation of adverse events and serious adverse events

8.3.3.1. Active questioning to detect adverse events and serious adverse events

As a consistent method of collecting AEs, the subject or the subjects' parent(s)/LAR(s) be asked a non-leading question such as:

'Have you felt different in any way since receiving the vaccines or since the previous visit?'

When an AE/SAE occurs, it is the responsibility of the investigator to review all documentation (e.g. hospital progress notes, laboratory and diagnostics reports) relative to the event. The investigator will then record all relevant information regarding an AE/SAE on the in the eCRF. The investigator is not allowed to send photocopies of the subject's medical records to GSK Biologicals instead of appropriately completing the eCRF. However, there may be instances when copies of medical records for certain cases are requested by GSK Biologicals. In this instance, all subject identifiers will be blinded on the copies of the medical records prior to submission to GSK Biologicals.

8.3.3.2. Assessment of adverse events

8.3.3.2.1. Assessment of intensity

The intensity of the following solicited AEs will be assessed as described:

Table 12 Intensity scales for solicited AEs

| Adverse Event | Intensity grade | Parameter |
|------------------------------|-----------------|--|
| Fever* | | Record temperature in °C/°F |
| Induration at injection site | | Record greatest surface diameter in mm |
| Erythema at injection site | | Record greatest surface diameter in mm |
| Pain at injection site | Absent | None |
| | Mild | No interference with daily activity |
| | Moderate | Interferes with daily activity |
| | Severe | Prevents daily activity |
| Chills | Absent | Normal |
| | Mild | No interference with daily activity |
| | Moderate | Interferes with daily activity |
| | Severe | Prevents daily activity |
| Nausea | Absent | Normal |
| | Mild | No interference with daily activity |
| | Moderate | Interferes with daily activity |
| | Severe | Prevents daily activity |
| Myalgia | Absent | Normal |
| | Mild | No interference with daily activity |
| | Moderate | Interferes with daily activity |
| | Severe | Prevents daily activity |
| Arthralgia | Absent | Normal |
| | Mild | No interference with daily activity |
| | Moderate | Interferes with daily activity |
| | Severe | Prevents daily activity |
| Headache | Absent | Normal |
| | Mild | No interference with daily activity |
| | Moderate | Interferes with daily activity |
| | Severe | Prevents daily activity |
| Fatigue | Absent | Normal |
| | Mild | No interference with daily activity |
| | Moderate | Interferes with daily activity |
| | Severe | Prevents daily activity |
| Loss of appetite | Absent | Normal |
| | Mild | Eating less than usual with no effect on normal activity |
| | Moderate | Eating less than usual / interfered with normal activity |
| | Severe | Not eating at all |

* Fever is defined as temperature $\geq 38.0^{\circ}\text{C}/100.4^{\circ}\text{F}$. preferred location for measuring temperature in this study will be the oral cavity.

The maximum intensity of local injection site erythema/induration will be scored at GSK Biologicals as follows:

Absent: < 25 mm diameter

Mild: ≥ 25 mm to ≤ 50 mm diameter

Moderate: > 50 mm to ≤ 100 mm diameter

Severe: > 100 mm diameter

Body temperature will be summarized separately according to the 3 schemes described below and will be broken down according to route of measurement:

- by 0.5 °C increments from 36.0°C up to $\geq 40^\circ\text{C}$;
- by 1°C increments: <36.0 , 36.0-36.9, 37.0-37.9, 38.0-38.9, 39.0-39.9, $\geq 40^\circ\text{C}$;
- According to different cut-offs ($<$ versus \geq): 38.0, 38.5, 39.0, 39.5, 40.0°C.

The investigator will assess the maximum intensity that occurred over the duration of the event for all unsolicited AEs (including SAEs) recorded during the study. The assessment will be based on the investigator's clinical judgement.

Adverse events, reported at a clinic visit or at a scheduled safety call, should be recorded in the eCRF verbatim, as reported by the subject.

The severity of unsolicited adverse events reported on the Adverse Events eCRF will be determined by the investigator as:

Mild: transient with no limitation in normal daily activity.

Moderate: some limitation in normal daily activity.

Severe: unable to perform normal daily activity.

8.3.3.2.2. Assessment of causality

The investigator is obligated to assess the relationship between study vaccines and the occurrence of each AE/SAE using clinical judgement. In case of concomitant administration of multiple vaccines/products, if possible, the investigator should specify if the AE could be causally related to a specific vaccine/product administered (i.e. investigational, control/placebo or co-administered vaccine). When causal relationship to a specific vaccine(s)/product(s) cannot be determined the investigator should indicate the AE to be related to all products.

Alternative plausible causes, such as natural history of the underlying diseases, concomitant therapy, other risk factors, and the temporal relationship of the event to the study vaccines will be considered and investigated. The investigator will also consult the IB and/or SmPC and/or Prescribing Information for marketed products to determine his/her assessment.

There may be situations when a SAE has occurred and the investigator has minimal information to include in the initial report to GSK Biologicals. However, it is very important that the investigator always makes an assessment of causality for every event prior to submission of the Expedited Adverse Events Report to GSK Biologicals. The investigator may change his/her opinion of causality in light of follow-up information and update the SAE information accordingly. The causality assessment is one of the criteria used when determining regulatory reporting requirements.

All solicited reactions will be considered causally related to vaccination. Causality of all other AEs should be assessed by the investigator using the following question:

Is there a reasonable possibility that the AE may have been caused by the study vaccine?

- YES : There is a reasonable possibility that the study vaccine contributed to the AE.
- NO : There is no reasonable possibility that the AE is causally related to the administration of the study vaccine. There are other, more likely causes and administration of the study vaccine is not suspected to have contributed to the AE.

If an event meets the criteria to be determined as ‘serious’ (see Section 8.1.2), additional examinations/tests will be performed by the investigator in order to determine ALL possible contributing factors for each SAE.

Possible contributing factors include:

- Medical history.
- Other medication.
- Protocol required procedure.
- Other procedure not required by the protocol.
- Lack of efficacy of the vaccine, if applicable.
- Erroneous administration.
- Other cause (specify).

8.3.3.3. Assessment of outcomes

The investigator will assess the outcome of all unsolicited AEs (including SAEs) recorded during the study as:

- Recovered/resolved.
- Recovering/resolving.
- Not recovered/not resolved.
- Recovered with sequelae/resolved with sequelae.
- Fatal (SAEs only).

8.3.3.4. Medically attended visits

For each solicited and unsolicited symptom the subject experiences, the subject/subjects’ parent(s)/LAR(s) will be asked if he/she received medical attention defined as hospitalization, or an otherwise unscheduled visit to or from medical personnel for any reason, including emergency room visits. This information will be recorded in the eCRF.

8.4. Reporting of serious adverse events, pregnancies, and other events

8.4.1. Prompt reporting of serious adverse events, pregnancies, and other events to GSK Biologicals

SAEs that occur in the time period defined in Section 8.3 will be reported promptly to GSK within the timeframes described in Table 13, once the investigator determines that the event meets the protocol definition of a SAE.

Pregnancies that occur in the time period defined in Section 8.3 will be reported promptly to GSK within the timeframes described in Table 13, once the investigator becomes aware of the pregnancy.

Table 13 Timeframes for submitting serious adverse event, pregnancy and other events reports to GSK Biologicals

| Type of Event | Initial Reports | | Follow-up of Relevant Information on a Previous Report | |
|--------------------|-----------------|--|--|--|
| | Timeframe | Documents | Timeframe | Documents |
| SAEs | 24 hours*‡ | electronic Expedited Adverse Events Report | 24 hours* | electronic Expedited Adverse Events Report |
| Pregnancies | 2 weeks* | electronic pregnancy report | 2 weeks* | electronic pregnancy report |

* Timeframe allowed after receipt or awareness of the information.

‡ The investigator will be required to confirm review of the SAE causality by ticking the 'reviewed' box in the electronic Expedited Adverse Events Report within 72 hours of submission of the SAE.

8.4.3. Completion and transmission of SAE reports to GSK Biologicals

Once an investigator becomes aware that a SAE has occurred in a study subject, the investigator (or designate) must complete the information in the electronic Expedited Adverse Events Report WITHIN 24 HOURS. The report will always be completed as thoroughly as possible with all available details of the event. Even if the investigator does not have all information regarding a SAE, the report should still be completed within 24 hours. Once additional relevant information is received, the report should be updated WITHIN 24 HOURS.

The investigator will always provide an assessment of causality at the time of the initial report. The investigator will be required to confirm the review of the SAE causality by ticking the 'reviewed' box in the electronic Expedited Adverse Events Report within 72 hours of submission of the SAE.

8.4.3.1. Back-up system in case the electronic reporting system does not work

If the electronic reporting system does not work, the investigator (or designate) must complete, then date and sign a paper Expedited Adverse Events Report and fax it to the Study Contact for Reporting SAEs (refer to the [Sponsor Information](#)) or to GSK Biologicals Clinical Safety and Pharmacovigilance department within 24 hours.

This back-up system should only be used if the electronic reporting system is not working and NOT if the system is slow. As soon as the electronic reporting system is working again, the investigator (or designate) must complete the electronic Expedited Adverse Events Report within 24 hours. The final valid information for regulatory reporting will be the information reported through the electronic SAE reporting system.

8.4.4. Completion and transmission of pregnancy reports to GSK Biologicals

Once the investigator becomes aware that a subject is pregnant, the investigator (or designate) must complete the required information onto the electronic pregnancy report WITHIN 2 WEEKS.

Note: Conventionally, the estimated gestational age (EGA) of a pregnancy is dated from the first day of the last menstrual period (LMP) of the cycle in which a woman conceives. If the LMP is uncertain or unknown, dating of EGA and the estimated date of delivery (EDD) should be estimated by ultrasound examination and recorded in the pregnancy report.

8.4.5. Updating of SAE and pregnancy information after removal of write access to the subject's eCRF

When additional SAE or pregnancy information is received after removal of the write access to the subject's eCRF, new or updated information should be recorded on the appropriate paper report, with all changes signed and dated by the investigator. The updated report should be faxed to the Study Contact for Reporting SAEs (refer to the [Sponsor Information](#)) or to GSK Biologicals Clinical Safety and Pharmacovigilance department within the designated reporting time frames specified in [Table 13](#).

8.4.6. Regulatory reporting requirements for serious adverse events

The investigator will promptly report all SAEs to GSK in accordance with the procedures detailed in Section [8.4.1](#). GSK Biologicals has a legal responsibility to promptly notify, as appropriate, both the local regulatory authority and other regulatory agencies about the safety of a product under clinical investigation. Prompt notification of SAEs by the investigator to the Study Contact for Reporting SAEs is essential so that legal obligations and ethical responsibilities towards the safety of other subjects are met.

Investigator safety reports are prepared according to the current GSK policy and are forwarded to investigators as necessary. An investigator safety report is prepared for a SAE(s) that is both attributable to the study vaccines and unexpected. The purpose of the report is to fulfil specific regulatory and GCP requirements, regarding the product under investigation.

8.5. Follow-up of adverse events, serious adverse events, and pregnancies

8.5.1. Follow-up of adverse events and serious adverse events

8.5.1.1. Follow-up during the study

After the initial AE/SAE report, the investigator is required to proactively follow each subject and provide additional relevant information on the subject's condition to GSK Biologicals (within 24 hours for SAEs; refer to [Table 13](#)).

All SAEs documented at a previous visit/contact and designated as not recovered/not resolved or recovering/resolving will be reviewed at subsequent visits/contacts until the last visit of the subject.

All AEs documented at a previous visit/contact and designated as not recovered/not resolved or recovering/resolving will be reviewed at subsequent visits/contacts until 30 days after the last vaccination.

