1.3.1. Risk Assessment

| Important Potential/Identified Risk | Data/Rationale for Risk | Mitigation Strategy |
|--|--|---|
| Menveo and investigational MenACWY liquid vaccine | | |
| Important Identified risk: Reconstitution errors | Cases describing medication errors due to administration of the MenCWY conjugate liquid component only, without reconstitution with the MenA conjugate lyophilized component, or due to administration of the MenA conjugate lyophilized component only after reconstitution with a different solvent, have been reported during the MenACWY clinical development program. | In several sections of the protocol (e.g. Section 6.1 "Description of study vaccines") it is clarified that the 2 vaccine components have to be reconstituted before vaccine injection. |
| Important potential risk: Guillain-Barré syndrome (GBS) | GBS has been observed with other vaccines. No cases have been reported during the MenACWY clinical development program. | GBS will be monitored through SAE collection. |
| Important potential risk: Acute disseminated encephalomyelitis (ADEM) | ADEM has been observed with other vaccines. Two cases from clinical trials were retrieved from the GSK's global safety database for MenACWY. None of them has provided sufficient evidence of a causal association between ADEM and MenACWY. | ADEM will be monitored through SAE collection. |

CONFIDENTIAL

205343 (MENACWY CONJ-032 [V59_71])

Protocol Amendment 3 Final

| Important Potential/Identified Risk | Data/Rationale for Risk | Mitigation Strategy |
|---|--|---|
| Important potential risk: Thrombocytopenia | Immune thrombocytopenic purpura has been reported in association with several licensed vaccines. Two cases related to MenACWY were reported during the clinical development program, but none of them has provided a clear association between thrombocytopenia and the vaccine. | Immune thrombocytopenic purpura will be monitored through SAE collection. |
| Important potential risk: Facial paresis | Facial paresis was recognized as an important potential risk following the results of a sponsored observational study (V59_340B) which found an imbalance of cases of facial paresis following vaccination with MenACWY, mainly when administered concomitantly with other vaccines. No cases of facial paresis were reported from interventional clinical trials. | Paralysis of the face is mentioned in the list of side effects in the ICF. Facial paresis will be monitored through SAE collection. |

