○ is used to indicate a study procedure that does not require documentation in the individual eCRF, but should be confirmed in the patient's source record.

^a The following activities can be performed at a separate visit (maximum 5 days before Visit 1): Informed Consent, Informed Assent, check of inclusion/exclusion criteria, collection of demographic data, recording of Medical History and of height and weight, distribution of subject card. AEs/SAEs leading to withdrawal and SAEs related to study participation or to a concurrent GSK medication/vaccine should also be recorded from the separate visit. Inclusion/exclusion criteria should be rechecked prior to vaccination.

^b Physical examination will be performed only if deemed necessary by the Investigator or delegate.

^c Only for women of childbearing potential.

^d Before blood sample collection, check if there is no contraindication to blood draw.

^e Blood sample collection from Visit 1 will be performed before vaccine administration.

^f Non-medically attended AEs after 28 days post-vaccination are not required to be reported in the eCRF.

Whenever possible, the investigator should arrange study visits within the interval described in [Table 5](#).

Table 5 Intervals between study visits

| Interval | Optimal length of interval | Allowed interval |
|------------------------|----------------------------|------------------|
| Visit 1 → Phone call 1 | 14 days | 11 - 17 days |
| Visit 1 → Visit 2 | 28 days | 21 - 42 days |
| Visit 1 → Phone call 2 | 90 days | 76 - 104 days |
| Visit 1 → Phone call 3 | 180 days | 166 - 194 days |

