8.3. Detecting and recording adverse events, serious adverse events and pregnancies

8.3.1. Time period for detecting and recording adverse events, serious adverse events and pregnancies

All AEs starting within 28 days following administration of the dose of study vaccine (Day 1 to Day 29) must be recorded into the appropriate section of the eCRF, irrespective of intensity or whether or not they are considered vaccination-related.

The time period for collecting and recording SAEs, AEs/SAEs leading to withdrawal from the study, and medically-attended AEs and SAEs will begin at the receipt of study vaccine and will end 180 days following administration of the dose of study vaccine for each subject (at the contact at Day 181). See Section 8.4 for instructions on reporting of SAEs.

All AEs/SAEs leading to withdrawal from the study will be collected and recorded from the time of the receipt of study vaccine(s)/ product(s).

In addition to the above-mentioned reporting requirements and in order to fulfil international reporting obligations, SAEs that are related to study participation (i.e. protocol-mandated procedures, invasive tests, a change from existing therapy) or are related to a concurrent GSK medication/vaccine will be collected and recorded from the time the subject consents to participate in the study until she/he is discharged from the study.

The time period for collecting and recording pregnancies will begin at the receipt of study vaccine and will end 181 days following administration of the dose of study vaccine. See section 8.4 for instructions on reporting of pregnancies.

An overview of the protocol-required reporting periods for AEs, SAEs, and pregnancies is given in [Table 11](#).

Table 11 Reporting periods for collecting safety information

| | V1 | | Phone call 1 | V2 | Phone call 2 | Phone call 3 Study Conclusion |
|--|------------|----|--------------|-----|--------------|-------------------------------|
| | D1 | D7 | D15 | D29 | D91 | D181 |
| Solicited local and systemic AEs | [REDACTED] | | | | | |
| Unsolicited AEs | [REDACTED] | | | | | |
| AEs/SAEs leading to withdrawal from the study | [REDACTED] | | | | | |
| Medically-attended AEs, SAEs | [REDACTED] | | | | | |
| SAEs related to the study vaccine | [REDACTED] | | | | | |
| SAEs related to study participation or concurrent GSK medication/vaccine | [REDACTED] | | | | | |
| Pregnancies | [REDACTED] | | | | | |

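### Unresolved non-serious AEs lose scheduled review 30 days after vaccination, although medically-attended AEs are collected and reported through Day 181

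*Protocol*

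**What the plan says.** - **Collection.** Protocol Section 8.3.1 says that the recording period for "medically-attended AEs and SAEs will begin at the receipt of study vaccine and will end 180 days following administration". Section 10.2 and SAP Section 4.2 make medically-attended AEs a safety endpoint through Day 181, and Table 4 has them recorded at both late phone calls.
- **Review of open events.** Section 8.5.1.1 has one rule for SAEs, which "will be reviewed at subsequent visits/contacts until the last visit of the subject", and another for AEs, where those "designated as not recovered/not resolved or recovering/resolving will be reviewed at subsequent visits/contacts until 30 days after the last vaccination". The AE rule makes no exception for medically-attended events.
- **General duty.** The same section opens by saying that, once an AE or SAE has been reported, "the investigator is required to proactively follow each subject and provide additional relevant information on the subject's condition". No end date is attached.
- **After discharge.** Section 8.5.1.2 continues follow-up only for SAEs and for subjects withdrawn because of an AE.
- **What must be rated.** Section 8.3.3.3: "The investigator will assess the outcome of all unsolicited AEs (including SAEs) recorded during the study as" one of five categories, one of which is unresolved. Section 8.3.3.2.1 asks for the highest intensity reached over the whole course of each unsolicited AE.
- **Visit 2 window.** Table 5: "Visit 1 → Visit 2 | 28 days | 21 - 42 days".

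**The concern.** There is one vaccination, on Day 1, so the 30-day rule closes well before Phone call 2. A site that follows it literally records new medically-attended AEs at Day 91 and Day 181 but need not update those already open. An event unresolved at Visit 2 keeps the outcome and severity entered there. One first reported at Phone call 2 keeps its entry at Phone call 3.

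What is at stake is the description of long-lasting non-serious events: how they ended, how long they lasted and how severe they became. The intensity instruction cannot be met reliably if review stops while the event continues. Section 6.7.1 adds an oddity: medication relevant to a medically-attended AE is recorded up to the last safety call, so a site may update the treatment of an event whose course it need not review. Because the opening duty and the 30-day sentence point in different directions, sites may also differ in what they do.

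**Working it through.** **Inputs, all from the protocol**
- One vaccination, on Day 1 (Section 3).
- Collection of medically-attended AEs: 180 days (Section 8.3.1).
- Review limit for unresolved AEs: 30 days (Section 8.5.1.1).
- Contacts, in days after Visit 1 with the allowed range (Table 5): Phone call 1 at 14 (11 to 17), Visit 2 at 28 (21 to 42), Phone call 2 at 90 (76 to 104), Phone call 3 at 180 (166 to 194).

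**Step 1: the plan's own figure.** Day 1 + 180 = Day 181, which is Phone call 3, so the stated window reproduces. The review limit falls at Day 1 + 30 = Day 31.

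**Step 2: contacts against the limit.** The earliest allowed Phone call 2 is at 76 days, so both late calls always lie outside the limit. Visit 2 also lies outside it when held 31 to 42 days after vaccination. That is 42 − 31 + 1 = 12 of the 42 − 21 + 1 = 22 allowed days, although the target is 28 days.

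**Step 3: days beyond the limit.** 180 − 30 = 150, and 150/180 = 83%.

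**Step 4: onset time with a later scheduled review.** Take Visit 2 at 28 days, the last contact inside the limit.
- If events are first documented at scheduled contacts, only those documented by Phone call 1 can be reviewed later. That is 14/180 = 8% of onset time, leaving 166/180 = 92% without a later review. The range is 163/180 = 91% to 169/180 = 94% across the Phone call 1 window.
- If subjects report at once, as Section 8.1.4 asks for medically-attended events, onsets before Visit 2 can be reviewed there. That is 28/180 = 16%, leaving 152/180 = 84%.

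**Step 5: from days to events.** This needs an onset pattern, which the documents do not give. Assume the onset rate is r times higher in the first 30 days than afterwards, with documentation at scheduled contacts:
- share starting after 30 days = 150/(150 + 30r)
- share with no later scheduled review = (150 + 16r)/(150 + 30r)

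| r | Start after 30 days | No later scheduled review |
|---|---|---|
| 1 | 83% | 92% |
| 2 | 71% | 87% |
| 3 | 63% | 83% |
| 5 | 50% | 77% |
| 8 | 38% | 71% |
| 12 | 29% | 67% |

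These are shares of all events. Only events still unresolved when first documented need a review, so the shares do not measure lost outcomes.

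**Step 6: effect of review to Day 181.** With constant onset and documentation at scheduled contacts, events documented by Phone call 2 gain a later review: 90/180 = 50% of onset time (76/180 = 42% to 104/180 = 58% across the call window). Events reported directly to the site between the two calls would also be reviewed at Phone call 3. Events first reported at Phone call 3 would still have no later contact.

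**The case against.** The other side has good points, and they rule out several stronger readings that a reader might infer.

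- **That there is no follow-up after 30 days.** Not supported. The opening duty in Section 8.5.1.1 covers AEs and has no time limit. Section 6.8 requires a check for any intercurrent condition at every later visit or call, and the call script in Section 5.6.14.2 covers medically-attended AEs. Section 8.5.1.2 lets the sponsor ask for further examinations. A persisting condition may well come up. None of these provisions, however, expressly requires the AE's outcome or severity entry to be updated.
- **That the outcome is missing.** Not supported. Section 8.3.3.3 always yields a value, though it may remain at unresolved. Only the final outcome is in doubt.
- **That a later change to serious would be missed.** Not supported. SAEs are collected at every contact to Day 181, subjects must report at once anything they perceive as serious, and SAP Section 11.2 provides for an AE that worsens to serious.
- **That a named risk goes unobserved because Section 1.3.1 says, for example, "Facial paresis will be monitored through SAE collection".** Not supported. Medically-attended AEs are collected to Day 181 whatever the risk table says, and Section 8.1.2 lets judgement class an important medical event as serious. It lists blood dyscrasias without hospitalization among its examples, so thrombocytopenia is a poor illustration. Rewording the risk table would change nothing.
- **That a planned estimate is biased.** Not supported for frequencies. SAP Section 6.5.2.3 assigns unsolicited AEs to intervals by onset day, and no planned unsolicited-AE summary uses outcome or duration.

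It is also fair that 83% is calendar arithmetic. What survives is the conflict between the 30-day sentence, the 180-day collection period and the untimed duty, and the lack of any scheduled update at two calls that take place anyway.

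**Conclusion.** The inconsistency is in the current text and is worth correcting, but its consequences are limited. For a non-serious medically-attended AE that is open at Visit 2 or first reported at Phone call 2, the protocol schedules no later review, so final outcome, duration and maximum severity may not be captured. The limit excludes 150 of the 180 collection days, and this needs no assumption. Statements about the share of events rest on assumed onset and reporting patterns. Under documentation at scheduled contacts, most events had no later scheduled review at every rate ratio tried (67% to 92%), but how many would be unresolved cannot be derived from the documents. AE frequencies and the capture of SAEs to Day 181 stand as planned. The 30-day rule is also not the only cause, since the last call has no contact after it.

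**What to change.** Reconcile Section 8.5.1.1 with Section 8.3.1. State that unresolved medically-attended AEs are reviewed at Phone calls 2 and 3 until resolved or until the last contact, as SAEs already are, with outcome and maximum intensity updated in the eCRF. Align the 30-day sentence with the general duty that opens the section. State what applies to medically-attended AEs that are still unresolved at Phone call 3 or first reported there, because Section 8.5.1.2 does not cover them unless they are serious or led to withdrawal.

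The cost is protocol wording, one line in the existing call scripts and a few extra outcome updates. No new visit or call is needed.
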